8. DATA REVIEW AND DATABASE MANAGEMENT

8.1. Site Monitoring

During the study, a contracted clinical research associate (monitor) will visit the site regularly to check the completeness of subject records, the accuracy of data, the adherence to the protocol and to GCP, the progress of enrollment, and to ensure that study drug is being stored, dispensed, and accounted for according to specifications. Key study personnel must be available to assist the contracted monitor during these visits.

The Investigator will maintain source documents for each subject in the study, consisting of case and visit notes containing demographic and medical information, laboratory data, ECGs, and the results of any other tests or assessments. All information in the database must be traceable to these source documents in the subject's file. The Investigator must also keep the original informed consent form signed by the subject (a signed copy is given to the subject).

The Investigator will give the monitor access to all relevant source documents to confirm their consistency with the database entries. Monitoring standards require full verification for the presence of informed consent, adherence to the inclusion/exclusion criteria, documentation of SAEs, and the recording of data that will be used for all primary and safety variables. Additional checks of the consistency of the source data with the database are performed according to the study-specific monitoring plan. No information in source documents about the identity of the subjects will be disclosed.

8.2. Database Management and Quality Control

Designated Investigator staff must enter the information required by the protocol into the study-specific database.

Subsequently, the entered data are systematically checked by Quality Assurance (QA) and data management staff, including 100% verification with source documentation. Errors or omissions are reconciled with the investigational site for resolution. Quality checking audits of all key safety and efficacy data in the database are made prior to locking the database.

9. DATA ANALYSIS

9.1. Subject Demographics and Other Baseline Characteristics

All data for background and demographic variables will be listed. Summary statistics will be provided for these parameters by subject. Relevant medical history, current medical conditions, results of laboratory screens, drug tests, and any other relevant information will be listed by subject.

9.2. Imaging Analysis and Statistics

Whole-body tomographic PET images created on the PET camera will be transferred to a dedicated PMOD (software for biomedical image quantification) workstation and reviewed visually for assessment of body organ distribution of radioactivity. Manually delineated dynamic

VOIs will be placed on the visually identified source organs and subsequently used for all the study PET frames. Activity within these VOIs is expressed in unit of total radioactivity. Radioactivity will be corrected for body attenuation, but not for decay, and time-activity curves (TACs) will be generated for each source organ. Following the last imaging time point residual radioactivity will be assumed to undergo physical decay only. Total number of disintegrations (ie, kinetic values or residence times) will be determined for each source organ either directly as the area under the curve of each TAC, or from modeling of acquired TACs in certain source organs (eg, gallbladder emptying, urinary bladder voiding, and GI tract modeling). These data will be utilized in the MIRDCalculations of target organ specific radiation absorbed dose with correction from urine assays and standard GI kinetic models (ICRP 2006) in Organ Level Internal Dose Assessment (OLINDA) (Stabin et al., 2005). Standard MIRDCalculations will be incorporated in dosimetry models for determination of radiation absorbed doses in target organs and whole-body (Harrison et al. 2015, ICRP 2007).

For whole-body biodistribution, the following parameters will be evaluated:

- Total source organ counts based on an individualized VOI template
- Source organ uptake and washout with calculation of the total number of disintegrations (or residence time) using the area under the time-activity curve divided by the injected dose of radiopharmaceutical
- Radiation absorbed dose estimates based on the MIRDCalculations methodology utilizing urine data in the model for increased accuracy of urinary bladder wall dose
- The ICRP 100 human alimentary tract (HAT) model will be applied to compute residence times in the small intestine, lower and upper large intestine

Descriptive statistics will be applied to describe biodistribution of [¹⁸F]GTP1 by organ.

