6.1.2. Whole-body [¹⁸F]GTP1 PET Imaging Visit

AEs will be continuously monitored during the Whole-body [¹⁸F]GTP1 PET Imaging Visit. All eligible subjects will be admitted to the overnight confinement unit on the day prior to the Whole-body [¹⁸F]GTP1 PET Imaging Visit, which will occur within 30 days of screening. Upon check-in, the following procedures will be performed:

- Urine drug, alcohol, and cotinine screening will be performed.
- A symptom-directed physical will be performed.

- Concomitant medications will be recorded.

On the day of imaging, procedures will be performed to ensure that the subject still meets the eligibility criteria. Prior to imaging the following procedures will be performed:

- Review of inclusion and exclusion criteria.
- Subject weight measurement will be obtained.
- Concomitant medications will be recorded.
- Vital signs will be taken just prior to imaging (after at least 5 minutes of rest in the sitting position), including systolic and diastolic BP, pulse rate, RR, and oral temperature.
- A 12-lead ECG will be performed.
- Blood samples will be collected for clinical chemistry and hematology, and a urine sample will be collected for urinalysis.
- Urine pregnancy test, if female of childbearing potential (which must be confirmed as negative within 24 hours prior to [¹⁸F]GTP1 injection).

The subject will have a venous catheter placed in the forearm for administration of [¹⁸F]GTP1, and the subject will lie supine on the camera in preparation for [¹⁸F]GTP1 administration. [¹⁸F]GTP1 will be administered as a bolus IV injection (See Section 5.2.2 for full details on [¹⁸F]GTP1 administration.). Immediately following [¹⁸F]GTP1 administration, PET acquisition will begin. PET scans will be acquired over approximately 6 hours, and the subject may have two breaks during the scanning period. A CT scan will be performed each time the subject lies on the camera. The following procedures will be performed during PET imaging:

- Vital signs will be taken, including systolic and diastolic BP, pulse rate, and RR (taken after at least 5 minutes of rest in the sitting position), approximately 20, 50, 80, and 120 minutes post-injection of [¹⁸F]GTP1.
- ECG will be taken approximately 25 and 45 minutes post-injection of [¹⁸F]GTP1, and at completion of PET imaging.

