6.2. Whole-body [^{18}F]GTP1 PET Imaging Procedures

Whole-body PET imaging will be performed on a Biograph 6 PET/CT camera acquiring an emission scan for each bed position and a CT scan will be performed each time the subject lies on the camera. Subjects will then receive a bolus IV administration of [^{18}F]GTP1 (See Section 5.2.2 for full details on [^{18}F]GTP1 administration.). Immediately following the [^{18}F]GTP1 administration a series of whole-body PET images from the vertex of the head to the thighs will be obtained over a period of up to 6 hours. The subject will have at least two breaks over a six-hour scanning session.

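### Do organ VOIs reused across all PET frames, and curves without decay correction, bias the residence times and washout in Section 9.2?

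*Combined protocol and SAP*

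**What the plan says.** Section 9.2 (Imaging Analysis and Statistics) begins with a visual review of the images. It then describes the regions as "Manually delineated dynamic" VOIs and continues: "VOIs will be placed on the visually identified source organs and subsequently used for all the study PET frames". The list of parameters in that section includes "Total source organ counts based on an individualized VOI template".

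On decay, Section 9.2 states: "Radioactivity will be corrected for body attenuation, but not for decay, and time-activity curves (TACs) will be generated for each source organ". After the last image only physical decay is assumed. Uptake and washout form one item together with the total number of disintegrations, which is the area under the curve divided by the injected dose. Some organs (gallbladder, urinary bladder, GI tract) may be modelled instead of integrated directly.

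On repositioning, Section 6.2 says "The subject will have at least two breaks over a six-hour scanning session" and "a CT scan will be performed each time the subject lies on the camera". Section 6.1.2 is looser on the breaks: "the subject may have two breaks during the scanning period". The synopsis and Section 3.1 require at least two. The synopsis study design names an isotope transmission scan at each re-entry; the synopsis procedures and Section 3.1 allow that or CT.

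**The concern.** Radiation dosimetry is the first objective. A person who gets up, voids and lies down again will not return to exactly the same position. If the VOIs stayed where they were drawn, activity outside them would be missed in every later frame. The last measured point, from which the tail is extrapolated, would be low as well. In a cold background this understates organ residence time and absorbed dose, which is the unsafe direction for a radiation estimate. Section 9.2 names attenuation correction but no co-registration or redrawing, although a new scan is taken at each re-entry.

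The second worry is that uptake and washout are listed as an outcome while only uncorrected curves are described. On such a curve even an organ that retains all its tracer falls steeply.

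**Working it through.** The plan gives no bias or precision figure to reproduce, and its sample size is not based on power. The documents do not give the F-18 half-life, the position shift, organ sizes or the break time. All are assumed below.

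**1. Loss from a VOI that is not moved.** Take a spherical organ of radius r in a cold background, with a tight VOI displaced by d:

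loss = 0.75(d/r) − (d/r)³/16

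With a half-life of 109.8 min, no biological clearance and a first break at 120 min, the share of the area after the break is 2^(−120/109.8) = 0.469. The fall in residence time is loss × 0.469.

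| r | d | loss in later frames | fall in residence time |
|---|---|---|---|
| 3 cm | 0.5 cm | 12.5% | 5.8% |
| 3 cm | 1 cm | 24.8% | 11.6% |
| 3 cm | 2 cm | 48.1% | 22.6% |
| 7 cm | 0.5 cm | 5.4% | 2.5% |
| 7 cm | 1 cm | 10.7% | 5.0% |
| 7 cm | 2 cm | 21.3% | 10.0% |

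For a wider range, let the break fall at 90 to 180 min and the biological half-life be 240 min or infinite. The late share is then 19% to 57%. A 10% to 30% loss in all later frames lowers residence time by 0.10 × 0.191 = 1.9% up to 0.30 × 0.567 = 17%.

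These figures hold only if the VOIs are left unadjusted. Spill-in from neighbouring organs, or VOIs drawn with a margin, would reduce them. They do not carry over unchanged to organs that are modelled or corrected with urine assays.

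**2. Does the text say the VOIs are left unadjusted?** The phrase about use in all frames fits two readings: the same coordinates throughout, or the same set of organ VOIs carried through the series and moved as needed. The word dynamic favours the second reading but is not defined. An individualized template says that VOIs are specific to the subject; it does not say that they stay fixed across camera sessions. The documents do not settle the matter.

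**3. Residence time from uncorrected curves.** Let λp = ln2/109.8 per min, λb = ln2 divided by the biological half-life, and λe = λp + λb. Per unit of uptake, with T = 360 min:

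- exact: 1/λe
- planned: (1 − e^(−λe·T))/λe + e^(−λe·T)/λp

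For a biological half-life of 240 min the planned value is 1.7454 h + 0.0962 h = 1.8416 h, against an exact 1.8114 h (+1.7%).

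| biological half-life | planned vs exact | decay-corrected 0–6 h area ÷ uncorrected |
|---|---|---|
| 60 min | +0.3% | 1.52 |
| 120 min | +1.2% | 1.86 |
| 240 min | +1.7% | 2.14 |
| 480 min | +1.4% | 2.32 |
| infinite | 0.0% | 2.53 |

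The small excess comes from the physical-decay tail and overstates dose slightly. Integrating decay-corrected curves would introduce a large error.

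**4. Washout.** With no biological clearance, the uncorrected curve stands at 2^(−360/109.8) = 0.103 at 6 h, an apparent washout of 90%. With a biological half-life of 240 min the figure is 1 − 0.103 × 2^(−360/240) = 96%. Decay-corrected, the two are 0% and 65%. Physical decay multiplies every organ's curve by the same factor at a given time, so ratios between organs and differences in rate constants do not change. Subtracting λp from the fitted rate recovers the biological rate exactly: 240 min goes in and 240 min comes out.

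**The case for a change.** The strongest case for a change is that one added sentence would settle the matter. No section mentions realignment, registration or an alignment check. *Dynamic* is undefined, and the wording around it leans toward reuse of one set, so two analysts could proceed differently. With at most 6 evaluable subjects, one misplaced VOI on a small organ could visibly move that organ's summary. Scans at each re-entry are already planned, so the cost is only analyst time.

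Much of this stands. The gap is real, Section 6.1.2's weaker wording on breaks does not remove it, and losses of the size shown would matter if they occurred. What does not stand is the step from an unwritten procedure to a biased result. The images are reviewed visually and the VOIs are drawn by hand, so a VOI lying off its organ after a break can be seen and corrected with the material at hand.

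On washout, it is fair that the plan does not say whether effective or biological clearance is meant. But no washout rate or half-life is defined as an endpoint, the item is tied to disintegrations, and the choice affects no dose.

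**Conclusion.** No change follows. The VOI point is a gap in written detail that image analysts fill sensibly: the documents neither state that VOIs stay fixed after re-entry nor rule out that they follow the organ. The possible understatement of organ residence time, about 5% to 12% for a 1 cm shift and 2% to 17% over the wider range, applies only if nobody adjusts the VOIs. It also rests on assumed shifts, organ sizes, break times and clearance, a cold background and tight VOIs.

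The decay point brings no gain. Uncorrected curves are correct for disintegrations and absorbed dose, within 2% in the scenarios run. Whether washout is reported as effective or biological clearance is a matter of labelling, and the second follows from the first by subtracting a known constant.

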2. STUDY OBJECTIVES AND ENDPOINTS

The overall goal of this protocol is to evaluate the biodistribution of [¹⁸F]GTP1 as a tau targeted radiopharmaceutical.

Objectives	Endpoints
To determine the radiation dosimetry of [¹⁸ F]GTP1 in Japanese subjects	
 ● Total source organ counts based on individualized organ volumes of interest (VOIs) ● Source organ uptake and washout with calculation of total number of disintegrations (or residence time, or kinetic values) using the area under the time-activity curve divided by the injected dose of radiopharmaceutical ● Radiation absorbed dose estimates based on the MIRD methodology utilizing urine data and International Commission on Radiological Protection (ICRP) gastrointestinal (GI) tract kinetics
To assess the safety and tolerability of a single dose of [¹⁸ F]GTP1 in healthy Japanese subjects	Safety will be evaluated by review of: 
 ● AEs ● Clinical laboratory tests ● Vital signs ● Physical findings ● ECG findings

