3. INVESTIGATIONAL PLAN

3.1. Study Design

This is an open-label study to evaluate the whole-body biodistribution of [¹⁸F]GTP1 in up to 6 evaluable healthy Japanese subjects (with at least 1 male and 1 female) to determine dosimetry for future studies. Subjects will be recruited by Invicro from the healthy population by advertising and community outreach. This study protocol requires each subject to complete the following visits: Screening Visit, Whole-body [¹⁸F]GTP1 PET Imaging Visit, and a Follow-up Phone Call. Screening evaluations will occur within 30 days of the Whole-body [¹⁸F]GTP1 PET Imaging Visit and may occur over multiple days. Screening procedures will include signing of the informed consent form, review of inclusion and exclusion criteria, collection of medical history and medication information, collection of demography information, physical examination, height and weight measurement, vital signs (respiratory rate, pulse rate, blood pressure [BP] and oral body temperature), laboratory tests (hematology, blood chemistry, and urinalysis), ECG, serum pregnancy test (if applicable), and drug and alcohol screening. Assessments will determine if the subject is medically stable to complete the study protocol and meets the eligibility criteria.

Subjects will be confined on the day prior to [¹⁸F]GTP1 imaging in the overnight confinement unit. On the day of check-in, the subjects will receive a symptom-directed physical assessment, drug and alcohol screening, and review of concomitant medications.

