4.2. Exclusion Criteria

Subjects fulfilling **any** of the following criteria are not eligible for inclusion in this study:

- The subject has a clinically significant abnormal laboratory value and/or clinically significant unstable medical or psychiatric illness.
- The subject is currently exposed to nicotine products or had regular nicotine exposure within a six-month period, to be verified by urine cotinine screening.
- History of drug or alcohol abuse within 12 months prior to screening, or evidence of such abuse as indicated by the laboratory assays conducted during the screening visit.
- The subject has evidence of clinically significant GI, cardiovascular, hepatic, renal, hematological, neoplastic, endocrine, neurological, immunodeficiency, pulmonary, or other disorder or disease.
- Prior participation in other research protocols or clinical care in the last year in addition to the radiation exposure expected from participation in this clinical study, such that radiation exposure exceeds the effective dose of 50 mSv, which would be above the acceptable annual limit established by the US Federal Guidelines.
- Use of any prescription drugs (except approved forms of birth control noted in Section 5.2.3), herbal supplements, within four weeks prior to initial dosing.
- Use of over the counter (OTC) medication (except acetaminophen), dietary supplements, or vitamins, within two weeks prior to initial dosing.
- Has a known hypersensitivity to any component of the formulation of [¹⁸F]GTP1 or related compounds.

- Major surgery, or donation or loss of 400 mL or more of blood within four (4) weeks prior to initial dosing, or longer if required by local regulation.
- Have a history or presence of any significant cardiovascular, respiratory, hepatic, renal, GI, endocrine, or neurological disorders which, in the opinion of the Investigator, are capable of altering the absorption, metabolism, or elimination of drugs or posing a health risk to participate in the study.
- History of immunodeficiency diseases, including a positive HIV test result.
- A positive Hepatitis B surface antigen (HBsAg) or Hepatitis C antibody test result.
- Positive pregnancy test result, if female. Women without documentation of non-childbearing potential will also receive pregnancy testing.
- Women who are lactating and breastfeeding.
- Unsuitable veins for repeated venipuncture.

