5.2.2. Administration of Investigational Agent

Study center personnel will administer [¹⁸F]GTP1 IV as a bolus injection. Prior to PET imaging, subjects will have an IV catheter (for radiotracer administration) inserted according to standard clinical practice. Each subject will receive a single injection of [¹⁸F]GTP1. The radioligand, [¹⁸F]GTP1, will be injected IV at a dose of not more than 370 MBq (≤10 mCi), with a maximum drug mass dose of 10 µg and maximum volume of 10 mL. The injection will occur as a bolus followed by a 10 mL saline flush. Qualified study staff will accompany subjects during PET imaging procedures.

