9.4. Sample Size

The sample size for this study was determined by practical considerations and is not based on statistical power calculations. Up to 6 evaluable subjects (with at least 1 male and 1 female) will complete this study.

While the sample size is small, this should be adequate to determine biodistribution and dosimetry calculations of [¹⁸F]GTP1 in Japanese subjects.

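### Must the dosimetry plan list effective dose and name a reference body model?

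*Combined protocol and SAP*

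**What the plan says.** Section 2 of the protocol lists three dosimetry endpoints: source organ counts, disintegrations (residence times), and "Radiation absorbed dose estimates based on the MIRD methodology utilizing urine data" together with ICRP gastrointestinal kinetics. Section 9.2 follows the same chain. Regions are drawn on the images, time-activity curves give residence times, and these enter the dose calculation with a urine correction and "standard GI kinetic models (ICRP 2006) in Organ Level Internal Dose Assessment (OLINDA"). The section then says that standard MIRD assumptions "will be incorporated in dosimetry models for determination of radiation absorbed doses in target organs and whole-body", citing the 2007 ICRP recommendations. Its statement on summaries is "Descriptive statistics will be applied to describe biodistribution of" the tracer by organ.

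Three other places bear on the point:

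- Section 3.1 says the study is done "to determine dosimetry for future studies".
- Section 4.2 excludes anyone whose exposure over the past year, added to that expected here, is "such that radiation exposure exceeds the effective dose of 50 mSv". It attributes the limit to US federal guidelines.
- Section 9.4 states "Up to 6 evaluable subjects (with at least 1 male and 1 female) will complete this study" and says the number was not based on a power calculation.

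**The concern.** Dosimetry is the first objective, and the result is meant to be reused. The protocol expresses its exposure limit as an effective dose in mSv, while its planned outputs stop at absorbed dose, which is a different quantity. A later study in Japanese subjects that applied the same screen would want effective dose per unit of injected activity, and the plan does not promise that number.

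If it is worked out afterwards, three choices appear to be open: the reference body model and whether it is scaled, the tissue weights, and how men and women are combined. Each would be made once the data from at most 6 people are known. A reader also could not tell from Section 9.2 alone whether a reported absorbed dose reflects the subject's body size as well as the tracer's kinetics.

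**Working it through.** **1. Where each quantity appears.**

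| Place | Quantity |
|---|---|
| Section 2, dosimetry endpoints | Counts, residence times, absorbed dose |
| Section 9.2, text and parameter list | Residence times, absorbed dose to organs and whole body |
| Synopsis, study design and outcomes | Same as Section 2 |
| Section 4.2 and synopsis, exclusion criteria | Effective dose, 50 mSv |

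In the text available for this check, effective dose occurs only in the last row. The text between the Section 1.1 background and Section 2 was not available, so nothing is claimed about exposure figures that may stand there.

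**2. Can effective dose be obtained from what is planned?**

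Effective dose per unit activity = [sum over organs of (tissue weight × organ dose)] / injected activity.

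- Organ doses are a planned output (Sections 2 and 9.2).
- Injected activity must be known, because residence time is defined as area under the curve divided by injected dose (Section 9.2).
- Tissue weights are not written out, but the 2007 ICRP recommendations are cited in Section 9.2.
- For a different body model, the residence times are endpoints, height and weight are measured (Section 6.4.3), and sex is recorded with the demographics.

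Every input that has to be measured is collected. The remaining inputs are published constants and a software setting.

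**3. Scale, from the protocol's own figures.** Section 5.2.2 allows injection "at a dose of not more than 370 MBq".

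- 50 mSv / 370 MBq = 0.135 mSv/MBq: the coefficient at which one maximum injection alone would reach the screening limit.
- 0.01 mSv/MBq × 370 MBq = 3.7 mSv.
- 3.7 / 50 = 7.4% of the limit.

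This is unit conversion, not an estimate for the tracer. It also leaves out the CT scans that Sections 6.1.2 and 6.2 require each time the subject lies on the camera.

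**4. Combining the sexes.** Six subjects with at least one of each sex permits a 1:5 split. The lone subject then carries weight 1/6 in a pooled mean and 1/2 in an average of the two sexes. If the minority-sex value exceeds the majority-sex value by a fraction d, the summaries are 1 + d/6 and 1 + d/2, a difference of d/3. The documents give no value for d, so no size is claimed.

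**5. Body mass.** Likewise, if organ self-dose is taken to vary inversely with mass, scaling matters when subject and model differ in mass. The documents state neither mass.

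**6. Can a late choice steer a conclusion?** The plan has no hypothesis test, no acceptance limit for dose and no power claim. There is no error rate to inflate and no pass or fail result to move.

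**The case for a change.** The strongest case for a change is that dosimetry in Japanese subjects is the reason for the study (Section 3.2), radiation is named as its main risk (Section 3.3), and the figure most useful to the next study is not promised. A citation does not define an output: Section 9.2 attaches the 2007 recommendations to a sentence about absorbed dose. The software is cited to a 2005 paper, which cannot show that the 2007 weights would be used. Adding the output would take one endpoint line and a few sentences, with no new scan or sample.

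Much of this stands. The text does not list effective dose or name a body model, and stating both would be tidy. What does not stand is the step from that to a fault. The 50 mSv rule is applied at entry, before this study's own dosimetry exists, so it does not depend on the study's output. Section 3.2 also says dosimetry studies have already been done in healthy subjects. The tissue weights matter only for a quantity the plan does not list, so they are not a separate defect. Since Section 9.2 invokes standard MIRD assumptions and announces no subject-specific scaling, the natural reading is conventional practice with an unscaled reference model.

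**Conclusion.** No change to the plan is needed. Followed as written, it yields sound residence times and absorbed doses for organs and whole body, and effective dose can be derived from them at any time. This is a gap that analysts would fill sensibly, and the study report is the natural place to state the model, software version and tissue weights used.

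No numerical error has been shown. The only scale the documents support is 0.135 mSv/MBq for a single maximum injection against the screening limit, and that is not a benchmark for the result. The effects of sex mix and body mass depend wholly on values the documents do not give and carry no weight here.

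The conclusion assumes that residence times are kept for each subject with sex and weight, and that the dosimetry summaries stay descriptive. If a later protocol set a pass or fail limit on this study's coefficient, the choice of model and weights would need to be fixed in advance there.
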